3.5.1.3 Handling plan for Intercurrent Events

Rescue medication use:

For subjects who take rescue medications defined in section 3.4.4 before Day 169, the data collected after administration of the rescue medications will not be included in the primary analysis. This approach attempts to reduce the confounding effects of rescue medications.

Treatment discontinuation:

Subjects who discontinue IP before Day 169 will be asked to come to scheduled evaluations until Day 169 visit and at least 3 months of off-treatment follow-up after the last IP administration. The data collected after discontinuation of study treatment will be included in the analysis.

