7.4 Prohibited and Restricted Therapies

Medications that are considered necessary for the safety and well-being of subjects may be given at the discretion of the Investigator, and recorded in the appropriate section of the eCRF. Use of treatments listed below may lead to IP discontinuation. Subjects should not start taking any of the following without discussing with the Investigator:

- 1. Naturopathic, herbal, or ayurvedic remedies.
- 2. Nutritional or dietary supplements
- 3. Vitamins and/or minerals.

7.4.1 Medications Leading to Immediate Discontinuation of Investigational Product for Both Populations

Receipt of any of these medications leads to immediate discontinuation of IP:

- Investigational agents
- Immunosuppressants with the exceptions listed below
- Biologic immunomodulators (including belimumab, abatacept, rituximab)
- Live or attenuated vaccines (the Sponsor recommends that Investigators ensure all subjects are up-to-date with required vaccinations prior to entry into the study)
- Plasmapheresis/Plasma exchange
- Any Ig therapy
- Corticosteroids > 0.5 mg/kg/day or > 40 mg/day prednisone-equivalent

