3.4.4 Prior and Concomitant Medications

Number (%) of subjects who receive prior medications and concomitant medications during Stage I and during Stage II + Off-treatment follow-up period will be summarized by world health organization (WHO) Drug dictionary Anatomical Therapeutic Chemical (ATC) category and PT. At each level of summarization, a subject is counted once if he/she reported one or more medications at that level. The summary of prior medications and concomitant medications during Stage I will be based on the safety analysis set. The summary of concomitant medications during Stage II + Off-treatment follow-up period will be based on the cross-over analysis set.

The prior and concomitant medications are defined as below.

- Prior medications are defined as medications with a stop date occurring before the first IP administration date.
- Concomitant medications during Stage I are defined as follows:
 - Medications with a start date before the Day 169 IP administration date and stop date on or after the first IP administration date for subjects entering Stage II.
 - Medications with a stop date on or after the first IP administration date for subjects not entering Stage II.

• Concomitant medications during Stage II + Off-treatment follow-up period are defined as medications with a stop date on or after the Day 169 IP administration date.

Use of disease-related medications at baseline, defined as all disease-related medications with an intake at the date of first dose of IP (ie, start date on or before the date of first dose and end date on or after date of first dose or ongoing) will be summarized for the full analysis set. The number and percentage of subjects who receive rescue medication during Stage I and during Stage II + Off-treatment follow-up period will also be summarized for the full analysis set and cross-over analysis set respectively.

Rescue medications for population #1 are listed below:

- Azathioprine (AZA) > 150 mg/day, methotrexate (MTX) > 20 mg/week, leflunomide >20 mg/day, mycophenolate mofetil (MMF) > 2gm/day OR any increase from baseline (including initiation of treatment)
- Any increase from baseline in anti-malarial (including initiation of treatment)
- Initiation of any new conventional disease-modifying anti-rheumatic drug (cDMARD)
- Oral prednisone > 10 mg/day OR any increase from baseline (including initiation of treatment)
- Intramuscular, IV, or intraarticular corticosteroids

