- Corticosteroids with a long biologic half-life (eg, dexamethasone, betamethasone)

Rescue medications for population #2 are listed below:

- Oral, intramuscular, IV, or intraarticular corticosteroids
- MTX, AZA, leflunomide, MMF, and other cDMARD or immunosuppressive or antiproliferative medications
- Any increase from baseline in anti-malarial (including initiation of treatment)
- Any increase or initiation of new doses of cevimeline or pilocarpine and cyclosporine eye drops (Restasis)

The missing start/stop date of medications will be imputed as appropriate and the details of the imputation will be included in the SPP.

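### Population #1: therapies that stop IP at once (biologics, Ig, plasma exchange, investigational agents) are not on the SAP rescue list, so users can count as ESSDAI responders and no planned analysis removes or penalises their later data

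*SAP*

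**What the plan says.** **Data rule.** SAP 3.5.1.3 has two rules for the primary analysis.
- Rescue: data are dropped "For subjects who take rescue medications defined in section 3.4.4 before Day 169". The reason given is: "This approach attempts to reduce the confounding effects of rescue medications".
- IP discontinuation: "The data collected after discontinuation of study treatment will be included in the analysis".

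**Rescue list, Population #1 (SAP 3.4.4).** AZA, MTX, leflunomide and MMF above set doses or increased; antimalarial increases; new conventional DMARDs; "Oral prednisone > 10 mg/day OR any increase from baseline (including initiation of treatment"); "Intramuscular, IV, or intraarticular corticosteroids"; and long-half-life corticosteroids.

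**Therapies that stop IP immediately (Protocol 7.4.1).** These include "Biologic immunomodulators (including belimumab, abatacept, rituximab"), "Immunosuppressants with the exceptions listed below", any Ig therapy, plasmapheresis or plasma exchange, investigational agents and high-dose corticosteroids. Protocol 7.4.3 defines Population #1 rescue through the restricted drugs of 7.4.2 only. The protocol's non-responder sentence for this population is also in 7.4.2, not 7.4.1.

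**Follow-up.** Under Protocol 6.6.1, a subject who stops IP before Day 169 keeps the scheduled visits to Day 169, completes at least 3 months off treatment, and then has an early discontinuation visit (EDV).

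**Response.** SAP 3.5.2.1 bars ESSDAI[3]/[4] response for premature discontinuation from the study or for rescue medication. Stopping IP is not itself a bar.

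**The concern.** Two subjects with added treatment are handled in opposite ways. One has a small prednisone increase: later ESSDAI data are dropped and the subject is a non-responder. The other is given rituximab on Day 60 with no listed drug: IP stops, ESSDAI data to Day 169 are analysed, and the subject can be a responder. The SAP's stated reason for dropping data, confounding by added therapy, applies to both.

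On the responder endpoint, any gain from the added therapy can be credited to the randomised arm. On the primary endpoint, use on placebo would shrink the difference and use on VIB4920 could inflate it. The planned sensitivity analyses do not show how much the result depends on these data.

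**Working it through.** **1. List comparison, Population #1**

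| Protocol 7.4.1 item | On SAP 3.4.4 list? |
|---|---|
| Biologic immunomodulators | No (only conventional DMARDs) |
| Ig therapy | No |
| Plasmapheresis/plasma exchange | No |
| Investigational agents | No |
| Immunosuppressants | Only if named or a conventional DMARD |
| High-dose corticosteroids | Yes, through the corticosteroid items |

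Live vaccines are also in 7.4.1 but are not at issue here. A user of an omitted therapy who also takes a listed drug is caught through that drug.

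**2. Planned analyses of the primary endpoint**

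| Analysis | Data after an omitted therapy |
|---|---|
| Primary MMRM (3.5.1.3) | Kept |
| Worst-score imputation (3.5.1.5) | Kept as observed; triggered by rescue only |
| All-data MMRM (3.5.1.5) | Kept |
| Time-adjusted AUC (3.5.1.5) | Kept |

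SAP 3.2 reports prohibited medication as a major deviation but attaches no data rule. Continuous secondary endpoints use the same handling (SAP 3.5.2.2).

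**3. Responder status.** Protocol 6.5 associates the EDV with premature discontinuation from the study, and Protocol 6.8 defines completion by Visit 15 (Day 365). In the Day 60 example the last dose is on Day 57. Taking 3 months as 12 weeks, 57 + 84 = Day 141, before Day 169, so the EDV could fall at about the Day 169 visit. If that is coded as premature study discontinuation, the subject is a non-responder. If not, the subject can be a responder. The SAP does not say which.

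**4. The plan's own power, reproduced.** Inputs from SAP 2.3: 36 per arm, difference 3.0, SD 5, two-sided alpha 0.10, t-test.
- Standard error = 5 × √(2/36) = 1.179; noncentrality = 3.0/1.179 = 2.546; df = 70.
- Noncentral-t power = 80.95%, against the stated 80%.
- Minimum detectable difference = 1.667 × 1.179 = 1.96, against the stated 2.0.

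**5. Size if the data are kept.** The documents give no frequency and no gain. Assume k users, all in one arm, each gaining g = 3 points (the size of the planned effect). The shift is k × g/36.

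| Users | Shift | Placebo users: difference, power | VIB4920 users: difference, rejection with no true effect |
|---|---|---|---|
| 0 | 0 | 3.00, 81.0% | 3.00, 10.0% |
| 1 | 0.083 | 2.92, 79.0% | 3.08, 10.1% |
| 3 (stress case) | 0.25 | 2.75, 74.7% | 3.25, 10.7% |

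Equal use and equal gain in both arms shifts the difference by 0. One user counted as a responder moves that arm's rate by 1/36 = 2.8 percentage points.

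**6. What excluding the data would do.**
- Precision: leaving three subjects out of one arm entirely gives a standard error of 5 × √(1/36 + 1/33) = 1.205, which is 2.2% larger. If the difference stays at 3.0, power is 79.4%.
- Bias: under missing at random (MAR), excluded VIB4920 users are projected as if drug benefit continued. If the full 3-point effect is in fact lost after IP stops, the difference exceeds its off-drug value by 3/36 = 0.08 for one user and 9/36 = 0.25 for three. If the new therapy also gives 3 points, gain and loss cancel, so keeping the data overstates the off-drug value by the same amount.

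**The case against.** The strongest reply is that these events already have a prespecified rule. Protocol 7.4.1 therapies stop IP; Protocol 10.5.1 and SAP 3.5.1.3 both keep data after IP stops; Protocol 7.4.3 confines rescue to the 7.4.2 drugs. The tiers also differ in substance, because a 7.4.2 drug may be taken while IP continues and a 7.4.1 therapy may not. This stands. A reader might infer that the SAP contradicts the protocol, or that the primary MMRM is wrong unless these data are excluded. The documents do not support that: keeping them is consistent treatment-policy handling, and exclusion under MAR is a different estimand that step 6 does not show to be better.

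A reader might also infer that the omitted therapies confound more than corticosteroids. The documents do not show this. Protocol 2.1.1 says no biologic or DMARD has been shown to reduce systemic activity significantly. That statement covers DMARDs too, however, and data after a new conventional DMARD are dropped, so it does not explain the different handling.

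The EDV point also stands in part: responder status is unsettled, not certain. But that coding could make IP discontinuers non-responders whatever they took, and the SAP should not leave the result to it.

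Finally, use would be visible in the deviation and concomitant-medication summaries. Visibility is not a prespecified analysis, and one chosen after unblinding would look data-driven.

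**Conclusion.** The gap is real but narrow. For Population #1, users of the omitted therapies can be ESSDAI[3]/[4] responders unless EDV coding happens to prevent it, and none of the planned analyses of the primary endpoint removes or penalises their later data. The primary MMRM rule itself is defensible and need not change.

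The size is unknown, and zero if nobody uses these therapies. Otherwise it is small: about 0.08 ESSDAI points per user in one arm, about 2 points of power per placebo user, and up to 2.8 percentage points on an arm's response rate. The first two figures rest on an assumed 3-point gain; the third assumes that the user would be counted as a responder.

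Population #2 is a minor matter. Its list includes "other cDMARD or immunosuppressive or antiproliferative medications", which may be read to cover biologics. Ig therapy, plasma exchange and investigational agents are not named, and the investigator-judgement item of Protocol 7.4.4, which 7.4.5 makes rescue, was not carried over.

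**What to change.** Before the interim unblinding:

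1. List the relevant 7.4.1 therapies in the SAP: biologic immunomodulators, Ig therapy, plasmapheresis or plasma exchange, investigational agents, and immunosuppressants other than permitted stable background treatment.
2. In SAP 3.5.2.1, count any subject who starts one before Day 169 as a non-responder. Their status then no longer depends on EDV coding.
3. In SAP 3.5.1.5, apply the worst-score rule to data after these therapies, and add a sensitivity analysis that excludes those data as for rescue. Keep the all-data analysis.
4. Excluding the data in the primary analysis is optional. If adopted, record it as an estimand choice that changes the retention rule of Protocol 10.5.1 for this subset, and state the MAR downside: up to 0.08 points for one VIB4920 user and 0.25 for three if benefit is fully lost. Protocol 4.2 reports that benefit in RA lasted 12 weeks after the last dose, so the loss may be smaller.

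The cost is a short list, slightly more analysis work and possibly a slightly lower response rate. Medications are already collected, and the SAP already extends the protocol's rescue list, for example with "Intramuscular, IV, or intraarticular corticosteroids" for Population #1.

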3.5.1.4 Handling plan for missing data

Missing data will be handled using the MMRM approach.

3.5.1.5 Sensitivity analysis of primary efficacy endpoint

The sensitivity analysis will be performed for the primary efficacy endpoint using the same model as the primary analysis with the following handling plan for the rescue medication use and treatment discontinuation.

- Impute result after rescue medications using the worst score on or before Day 169 including baseline. Include data collected after discontinuation of study treatment.
- Include data collected after rescue medications and data collected after discontinuation of study treatment.

In addition, the primary efficacy endpoint will be analyzed based on the time adjusted area under the curve (AUC) of change from baseline. First, the AUC of the ESSDAI and ESSPRI score from baseline to Day 169 will be calculated using the trapezoidal rule. Second, the time adjusted AUC will be obtained by dividing the AUC by the total time for baseline. Third, time adjusted AUC of change from baseline will be calculated by subtracting the baseline score from the time adjusted AUC. All observed data including data collected after rescue medications will be used to calculate the time adjusted AUC. The time adjusted AUC of change from baseline will be analyzed using MMRM approach including fixed effects for treatment, visit, visit by treatment interaction, and corresponding baseline score.

3.5.1.6 Subgroup analyses of primary endpoint

3.5.1.7 Multiplicity adjustment

There is no multiplicity issue for the primary endpoint analysis for each population because there is only one primary comparison (VIB4920 1500mg vs placebo) for each population.

3.5.1.8 Additional analysis

The change from baseline in ESSDAI for population #1 and change from baseline in ESSPRI for population #2 will be analyzed for Stage II + Off-treatment follow-up period based on the cross-over analysis set using the same MMRM model as the primary analysis. Data collected after rescue medications and after discontinuation of study treatment will be included.

The change from baseline in modified ESSDAI excluding peripheral nervous system, central nervous system, and pulmonary domains for population #1 will be analyzed using MMRM approach for Stage I and Stage II + Off-treatment follow-up period based on the full analysis set and cross-over analysis set respectively. The model will include fixed effects for treatment, visit, visit by treatment interaction, and baseline modified ESSDAI score. The handling plan for rescue medication use and treatment discontinuation for Stage I analysis is the same as those for the primary (section 3.5.1.3) and sensitivity (section 3.5.1.5) analyses of the primary efficacy endpoint. Data collected after rescue medications and after discontinuation of study treatment will be included for the Stage II + Off-treatment follow-up period analysis.

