7.2 Treatment Assignment and Bias Minimization

7.2.1 Treatment Allocation

Subjects will be randomized in a 1:1 ratio to receive either VIB4920 or placebo.

IP (VIB4920 or placebo) must be administered the same day the IP is assigned. If there is a delay in the administration of IP such that it will not be administered within the specified timeframe, the study monitor must be notified immediately.

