3.1.1 Definition of Baseline

Unless otherwise specified, baseline will be defined as the last non-missing valid observation prior to the first administration of IP. In cases where baseline measurements are taken on the same day as IP and no times are reported, it will be assumed that these measurements are taken prior to IP being administered.

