3.3 Analysis Sets

3.3.1 Full analysis set

The full analysis set includes all randomized subjects who received any dose of IP. Subjects will be analyzed according to the treatment randomized. The efficacy analysis will be based on the full analysis set.

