3.3.4 Cross-over analysis set

The cross-over analysis set includes all subjects who received any dose of IP during Stage II of the study.

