3.5.2 Secondary Efficacy Endpoints and Analyses

3.5.2.1 Secondary efficacy endpoints

The secondary efficacy endpoints are as follows:

• Change from baseline in ESSPRI at Day 169 (population #1)

• Proportion of subjects achieving ESSDAI[3] and ESSDAI[4] response, defined as a decrease of at least 3[4] points from baseline in the ESSDAI at Day 169 without premature discontinuation from the study and without receiving rescue medications (population #1)

• Proportion of subjects achieving ESSPRI response, defined as ≥ 1 point or 15% reduction from baseline in ESSPRI score at Day 169 without premature discontinuation from the study and without receiving rescue medications (population #2)

- Change from baseline in FACIT-Fatigue score at Day 169 (population #1 and #2)
- Change from baseline in OSDI at Day 169 (population #1 and #2)
- Change from baseline in PGIS at Day 169 (population #1 and #2)

FACIT-Fatigue:

The FACIT-Fatigue is a 13-item questionnaire, subject-completed, used to assess the impact of fatigue. Its recall period is 7 days. The responses range from 0 (Not at all) to 4 (Very Much). To calculate the total score, the negatively stated items are reversed by subtracting the response from "4". Final scores are the sum of the responses and range from 0 to 52. Higher scores indicate better quality of life.

OSDI:

OSDI is a valid and reliable instrument for assessing effect on vision-related function and dry eye disease severity (normal, mild, moderate, and severe). Its recall period is 1 week. It is composed of 12 questions that the physician asks the subject and circles the number that best represents each question. The responses for each question range from 0 (None of the time) to 4 (All of the time). The OSDI score is calculated as follows:

OSDI score = (sum of scores for questions answered) / (number of questions answered) \times 25

The OSDI score ranges from 0 to 100 with higher scores signifying greater disability.

PGIS:

The PGIS is a single item designed to capture the subject's perception of overall symptom severity over the past week on a 5-point categorical response scale (none, mild, moderate, severe, very severe).

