3.5.2.2 Secondary efficacy analysis

The continuous secondary efficacy endpoints of population #1 and population #2 will be analyzed based on Stage I data for the full analysis set using the MMRM approach, with treatment, visit, visit by treatment interaction, randomization stratification factor, and corresponding baseline value. Handling plan for the rescue medication use and treatment discontinuation will be the same as those described for the primary endpoints in sections 3.5.1.3 and 3.5.1.5.

The details of these analyses and presentations of results will be the same as those described for the primary endpoints in section 3.5.1.2.

The analysis for Stage II + Off-treatment follow-up period will be performed using the same MMRM approach based on the cross-over analysis set. Data collected after rescue medications and after discontinuation of study treatment will be included.

The binary secondary efficacy endpoints of population #1 and population #2 will be analyzed for the full analysis set using a logistic regression model, with treatment and corresponding baseline score included in the model.

The estimated treatment effect (ie, the odds ratio for VIB4920 versus placebo), corresponding 90% CI, and 2-sided p-value will be presented. In addition, the response rate and the corresponding 90% CI within each treatment group will be presented. Longitudinal presentations of results over time up to Day 169 will be created using full analysis set. In addition, the analysis will be produced for Stage II + Off-treatment follow-up period separately using the cross-over analysis set.

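### Stage II changes in the placebo-to-VIB4920 group are measured from before the placebo period; a supplementary Day 169 pre-dose baseline would isolate change after the first VIB4920 dose

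*SAP*

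**What the plan says.** SAP 3.1.1 gives the general rule: "baseline will be defined as the last non-missing valid observation prior to the first administration of IP", unless a section specifies otherwise. Placebo is IP, as Protocol 7.2.1 shows: "IP (VIB4920 or placebo) must be administered the same day the IP is assigned". For a subject randomized to placebo, baseline is therefore the Day 1 value (or an earlier one if Day 1 is missing). At Day 169 the two arms exchange drug (SAP 2.2.1).

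For Stage II plus follow-up, SAP 3.5.1.8 says the primary variables "will be analyzed for Stage II + Off-treatment follow-up period based on the cross-over analysis set using the same MMRM model as the primary analysis". SAP 3.5.2.2 does the same for the continuous secondary endpoints. For the binary ones it says: "The estimated treatment effect (ie, the odds ratio for VIB4920 versus placebo), corresponding 90% CI, and 2-sided p-value will be presented", and then: "In addition, the analysis will be produced for Stage II + Off-treatment follow-up period separately using the cross-over analysis set". Laboratory, vital sign, ECG and weight changes are also summarized for Stage II (SAP 3.6.2, 3.6.3.2 to 3.6.3.4). None of these sections names a Stage II baseline.

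On grouping, the full analysis set has a rule: "Subjects will be analyzed according to the treatment randomized". The set used for Stage II is defined by membership only: "The cross-over analysis set includes all subjects who received any dose of IP during Stage II of the study".

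Protocol 4.2 gives Stage II several purposes. One is to learn how leaving out the Day 15 induction dose affects the speed and size of the biologic response. Another is to follow duration of response in the arms first given VIB4920.

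**The concern.** Stage II is where the placebo half of the trial first receives VIB4920. The SAP plans within-group results there: least-squares means per group (3.5.1.2, carried over by the use of the same model), response rates with 90% CIs (3.5.2.2), and laboratory shifts (3.6.2). In the placebo-to-VIB4920 group each is counted from a point 168 days (24 weeks) before the first VIB4920 dose. A subject can meet a response or shift criterion before receiving any VIB4920 and still be counted in a Stage II table. Having the Day 1 score as a covariate does not change this, because the outcome is still change from Day 1. The induction-dose question in Protocol 4.2 needs change since the first VIB4920 dose, and these tables do not give it.

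**Working it through.** **Plan's own figures.** SAP 2.3 assumes SD 5 and difference 3.0 for ESSDAI, SD 2 and difference 1.0 for ESSPRI, two-sided alpha 0.10, 80% power. n per arm = 2(1.645 + 0.842)² × (SD/difference)² gives 35 and 50; the exact t-test gives 36 and 51, as stated. Minimum detectable differences are 1.96 and 0.66, against the stated 2.0 and 0.66. The figures reproduce. The point does not depend on them; only the SDs are used below.

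**Which outputs use the Day 1 baseline in Stage II.**

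| Stage II output | Anchor in the visible SAP |
|---|---|
| ESSDAI, modified ESSDAI, ESSPRI, FACIT-Fatigue, OSDI, PGIS change; responder status | before first IP (3.1.1) |
| Laboratory change and shift; vital sign and weight change | before first IP |
| Adverse events | first Stage II dose, or first VIB4920 dose (Table 3) |
| ADA, whole study | first VIB4920 dose (3.8) |
| Observed values, worst toxicity grade, absolute vital sign and QTc limits | no change from baseline involved |

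The SAP thus re-anchors adverse events and ADA, but not the change scores.

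**Decomposition.** For a visit t after Day 169:

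change from Day 1 = (Day 169 − Day 1) + (t − Day 169).

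In the placebo-to-VIB4920 group the first term arose on placebo. The documents give no placebo change, so it is assumed here over a range and taken to persist.

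| Population | Assumed placebo change | Assumed change after Day 169 | Read from Day 1 | Read from Day 169 |
|---|---|---|---|---|
| #1 ESSDAI | 0, -2, -4 | -3 | -3, -5, -7 | -3 each time |
| #1 ESSDAI | 0, -2, -4 | 0 | 0, -2, -4 | 0 each time |
| #2 ESSPRI | 0, -0.5, -1 | -1 | -1, -1.5, -2 | -1 each time |

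In the first row the share that arose on placebo is 0%, 2/5 = 40% and 4/7 = 57%. These shares only restate the chosen inputs.

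**Response already met at Day 169, before any VIB4920.** With normal change of mean m, P = Φ((−threshold − m)/SD):

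- ESSDAI[3], m = 0, -2, -4: Φ(−0.6), Φ(−0.2), Φ(0.2) = 27%, 42%, 58%.
- ESSDAI[4], same m: Φ(−0.8), Φ(−0.4), Φ(0) = 21%, 34%, 50%.
- ESSPRI, 1-point rule, m = 0, -0.5, -1: Φ(−0.5), Φ(−0.25), Φ(0) = 31%, 40%, 50%.

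ESSDAI takes whole-number values. A half-point correction moves the ESSDAI[3] range to about 31% to 62% and the ESSDAI[4] range to about 24% to 54%. The entries at m = 0 reflect variability, not improvement. Counting rescue users as non-responders would lower all of them.

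**Data available.** The note to Protocol Table 2 requires dosing-day assessments to be done before the dose unless otherwise specified. SAP 3.1.2 limits the Day 169 window to the dose date or earlier. That limit works by date, and Protocol 7.1.1.4 also has vital signs taken during and after the Day 169 infusion, so a vital sign baseline must be restricted to pre-infusion readings. After Day 169 the only scheduled ECG is at Day 365 or early discontinuation. For completers that is 365 − 281 = 84 days after the last scheduled dose.

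**The case against.** Four arguments go the other way, and much of each stands.

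- Day 1 is a legitimate Stage II baseline. It serves duration of response and the comparison of randomized sequences, and SAP 3.5.1.8 is headed as an additional analysis. A reader might infer that the Stage II model is wrong or its between-sequence contrast biased by the choice of baseline. The documents do not support that.
- A reader might infer that Stage II treatment is undefined. It is mainly a labelling gap. Every Stage II entrant switches, so coding by randomized arm or by current drug forms the same two groups (misdosing apart), and reusing the primary model points to the randomized factor. What remains is the sign: with an assumed effect of -3 in each stage and none retained after the switch, the contrast is +3 under one coding and -3 under the other. Keeping the VIB4920-versus-placebo label after the switch invites misreading.
- It cannot be said that no planned table anywhere isolates change on VIB4920. Exploratory and biomarker sections are redacted and the statistical programming plan is not available. The visible SAP, however, refers to that plan for visit windows and medication dates, not for baseline.
- Stage I placebo results at Day 169 can be set against Stage II results. This is only approximate: Stage I uses all treated subjects and Stage II only those who entered it, and the primary analysis drops post-rescue data while Stage II keeps them. The sensitivity analysis that keeps post-rescue data removes the second difference, not the first.

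**Conclusion.** The point holds as a cheap improvement. On the visible text, Stage II within-group changes, response rates and laboratory, vital sign and weight changes or shifts in the placebo-to-VIB4920 group mix placebo-period change with change on VIB4920, and no visible planned table isolates the second part. The primary Day 169 analyses, Stage I, adverse event and ADA analyses, and outputs not based on change, are unaffected.

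The size is unknown. It equals whatever placebo-period change persists into Stage II. The percentages above are illustrations under assumed placebo means and a normal model; they are neither estimates nor bounds, and they are not Stage II response rates, because response can be lost later. A reader might also infer that Stage II QTc increases need a new baseline. They do not, since no ECG is scheduled during Stage II dosing after Day 169.

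Change from Day 169 is itself uncontrolled. It removes the placebo-period component but does not give a causal effect of VIB4920.

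**What to change.** 1. Add to SAP 3.1.1: *Stage II baseline is the latest valid, non-missing value taken before the first Stage II infusion starts (Day 169, pre-dose). The existing rule for same-day values without a time applies. For vital signs, only pre-infusion readings qualify.*
2. Add supplementary, separately labelled Stage II tables of change from this baseline for laboratory, vital sign and weight data. For the placebo-to-VIB4920 sequence, add descriptive change from Stage II baseline, stated to be uncontrolled, for ESSDAI, modified ESSDAI, ESSPRI, FACIT-Fatigue, OSDI and PGIS. Show Stage II response rates beside the Day 169 pre-dose rate in the same Stage II entrants.
3. Keep the Day 1-based analyses. In SAP 3.3.4 and 3.5.2.2, label Stage II groups and contrasts by randomized sequence (VIB4920-to-placebo, placebo-to-VIB4920) instead of VIB4920 versus placebo.

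No ECG change is needed.

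The cost is SAP wording and some extra tables; all values are already scheduled. The downside is a second baseline to label. In the VIB4920-to-placebo sequence that baseline is an on-drug value, so its column shows change after the switch to placebo and should say so.
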